### **8.3 Summary and Analysis of Percentage of Subjects With Titers Above LLOQ**

#### **8.3.1 Primary Endpoint**

This endpoint will be summarized for PPS3.

The percentage of subjects with titers above the LLOQ as well as the associated 2-sided 80% Clopper-Pearson CIs [Clopper, 1934] will be computed by study group at AVISIT 4.

In addition, differences in percentages of subjects with titers above the LLOQ and 2-sided 80% CIs between selected study groups will be calculated using the method of Miettinen and Nurminen [Miettinen, 1985]. The following differences will be calculated:

- rMenBOMV+ACWY\_S versus rMenBOMV+ACWY\_D (test for immune interference, due to immunological stress to lymph node)
- MenABCWY versus rMenBOMV+ACWY\_S (test for other unknown immunological interference)
- rMenBOMV+ACWY\_S versus rMenBOMV
- rMenBOMV+ACWY\_S versus MenACWY
- rMenBOMV+ACWY\_D versus rMenBOMV
- rMenBOMV+ACWY\_D versus MenACWY
- MenABCWY versus rMenBOMV
- MenABCWY versus MenACWY

No adjustments will be made for multiple comparisons.

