### **10.4. *Determination of sample size***

The sample size is for exploratory statistical analysis purposes only. There are no formal confirmatory hypotheses to be tested. The text in this section describes what can be observed with the current sample size.

Sample size calculation was performed using PASS 12 and SAS 9.2 (SAS Institute Inc., Cary, NC, USA).

The potential immune interference due to immunological stress to lymph nodes is assumed to result in decreases to all of the 4 B test strains but to various extents. In a previous study (MenABCWY-011 [V102\_15]), the GMT ratios ranged from 74% (-0.13 on log10 scale) to 50% (-0.3 log10 scale) with a mean of 64% (-0.19 on log10 scale). Because of this consistent decrease in GMT ratios in the MenABCWY group in comparison to the MenB group across the 4 serogroups, the presence of the lymph-node effect will be tested globally on all the serogroups together. A multivariate analysis of V102\_15 data provided an estimate of  $\sigma = 0.435$  (on log10 scale) for the standard deviation (SD) of the averaged GMTs across the 4 serogroups of the MenABCWY arm. That variability is higher than what would be expected by dividing the variance of a single serogroup by 4 due to the correlations existing between serogroups.

Therefore, assuming a SD of  $\sigma = 0.435$  (in log form), group sample sizes of 100 in each study group will achieve a power of approximately 80% to reject the null hypothesis of equal means when the population mean difference is -0.130 (log GMT ratio 74%) with a SD of 0.435 for both groups and a significance level (alpha) of 10% using a 1-sided 2-sample equal-variance t-test. This calculation ignores the potential correlation that might exist between serogroups of the MenABCWY when pooled together.

The numerical results for the 2-sample t-test assuming equal variance (alternative hypothesis:  $\delta < 0$ ) is shown in [Table 14](#).

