**Analysis of Percentage of Subjects With Titers Above LLOQ and a 4-fold Increase**

The percentage of subjects with titers above the LLOQ and a 4-fold increase as well as the associated 2-sided 80% Clopper-Pearson CIs will be computed by study group at each visit [Clopper, 1934]. In addition, differences in percentages and 2-sided 80% CIs between the groups will be calculated and the associated CI for the difference will be constructed using the method of Miettinen and Nurminen [Miettinen, 1985].

Unadjusted and adjusted GMTs and associated 2-sided 80% CIs will be computed for each group and for each strain at each visit. For each study group, adjusted GMTs and their 80% CIs will be obtained by exponentiating (base 10) the least square means and the lower and upper limits of the 80% CIs of the log-transformed titers (base 10).

The fixed-effect model for the individual serogroups/strains will include the age strata, treatment, and center as fixed effects. The fixed-effect model for the pooled analysis will include the age strata, treatment, strain, and center as fixed effects. The pre-vaccination log-transformed titer with centering at zero will be included as a continuous covariate. An interaction between serogroup and pre-vaccination log-transformed titer centered at zero will be included in the model.

Additionally, the group GMT ratios will be computed. The 2-sided 80% CIs for the group GMT ratio will be constructed by exponentiating the group difference of the least squares means of the log-transformed titers and the lower and upper limits of the 80% CI.

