## 3 Investigational Plan

### 3.1 Overall Study Design and Plan

This is a Phase II, randomized, open-label, controlled, multi-centric study with 5 parallel study groups. The enrollment will be performed to ensure equal distribution of the population across two age strata of 10 to 17 years and 18 to 25 years in each study group. Within each stratum the randomization algorithm will use a minimization procedure accounting for center. Approximately 500 subjects will be randomly assigned at a 1:1:1:1:1 ratio to one of five study groups:

[figure not shown]
1. MenABCWY: Approximately 100 subjects (50 subjects aged 10 to 17 years and 50 subjects aged 18 to 25 years) will receive 1 intramuscular (IM) dose of MenABCWY twice, 2 months apart.
2. rMenBOMV+ACWY\_S: Approximately 100 subjects (50 subjects aged 10 to 17 years and 50 subjects aged 18 to 25 years) will concomitantly receive 1 IM dose of rMenB+OMV NZ and 1 IM dose of MenACWY in the same arm (approximately 2.5 cm apart) twice, 2 months apart.
3. rMenBOMV+ACWY\_D: Approximately 100 subjects (50 subjects aged 10 to 17 years and 50 subjects aged 18 to 25 years) will concomitantly receive 1 IM dose of rMenB+OMV NZ and 1 IM dose of MenACWY in 2 different arms twice, 2 months apart.

4. rMenBOMV: Approximately 100 subjects (50 subjects aged 10 to 17 years and 50 subjects aged 18 to 25 years) will receive 1 IM dose of rMenB+OMV NZ twice, 2 months apart.
5. MenACWY: Approximately 100 subjects (50 subjects aged 10 to 17 years and 50 subjects aged 18 to 25 years) will receive 1 IM dose of MenACWY once.

Details of the injection site location(s) can be found in Table 9.

The study design diagram is provided in Figure 1.

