#### **4.2 Randomization, Stratification, and Blinding**

Randomization will be performed within 5 days prior to or at Visit 1 (Day 1). The randomization list will be generated using MATerial Excellence (MATEX). Central randomization will be performed using the Source DataBase for Internet Randomization (SBIR) system. Within each age stratum (10 to 17 years and 18 to 25 years) the randomization algorithm will use a minimization procedure accounting for center.

This is an open-label study. Only the laboratory in charge of the laboratory testing will be blinded to the treatment, subject, and visit number, and codes will be used to link the subject, visit, and study (without any link to the treatment attributed to the subject) to each sample.

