### ANCOVA1

- The fixed-effect model will include age strata, study group, and center as fixed effects. The pre-vaccination (Baseline) log-transformed titer with centering at zero will be included as a continuous covariate.
- The model will be fitted to each serogroup/strain\* separately.

\* a categorical variable will be used to indicate if the dependent variable (response) is for serogroup A, C, W-135, Y or individual serogroup B test strain M14459, 96217, NZ98/254 or M07-0241084.

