## **8.4 Summary and Analysis of Percentage of Subjects With a 4-fold Increase in hSBA Titer**

### **8.4.1 Primary Endpoint**

This endpoint will be summarized for PPS3.

The analysis described in Section 8.3 will be repeated for subjects with a 4-fold increase in hSBA titer at AVISIT 4 since Baseline.

A 4-fold increase is defined as:

- a) for individuals whose pre-vaccination titers are < LOD, the post-vaccination titers must be  $\geq$ 4-fold the LOD or  $\geq$  the LLOQ, whichever is greater;
- b) for individuals whose pre-vaccination titers are  $\geq$  the LOD and < the LLOQ, the post-vaccination titers must be at least 4 times the LLOQ;
- c) for individuals whose pre-vaccination titers are  $\geq$  the LLOQ, the post-vaccination titers must be at least 4 times the pre-vaccination titer.

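### The responder-rate differences name no age stratification although allocation is stratified by age; if response differs by age, the 80% intervals are valid but somewhat wider than necessary

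*SAP*

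**What the plan says.** **Allocation.** SAP 4.2: "Within each age stratum (10 to 17 years and 18 to 25 years) the randomization algorithm will use a minimization procedure accounting for center". SAP 3.1 plans each group of about 100 as "50 subjects aged 10 to 17 years and 50 subjects aged 18 to 25 years". Protocol 5.2.2.1.1 adds that enrollment is frozen for an age stratum in a group once 50 subjects are reached, and that site staff supply the age category when they request the allocation.

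**GMTs and GMRs.** For ANCOVA1 (SAP 8.1.1), "The fixed-effect model will include age strata, study group, and center as fixed effects", with baseline log titer as a covariate. ANCOVA2, for the pooled B strains, also carries age stratum, and SAP 8.2.1 reuses ANCOVA1 for the GMRs.

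**Responder percentages.** Both percentages are listed as primary endpoints (SAP 3.2.1) and again as secondary endpoints one month after the first vaccination (SAP 3.2.2). In SAP 8.3.1, differences in percentages with 2-sided 80% intervals "between selected study groups will be calculated using the method of Miettinen and Nurminen"; SAP 8.3.2 uses the same method. SAP 8.4.1 carries this over: "The analysis described in Section 8.3 will be repeated for subjects with a 4-fold increase in hSBA titer at AVISIT 4 since Baseline"; SAP 8.4.2 does the same at AVISIT 2. Protocol 10.8 agrees: "the associated CI for the difference will be constructed using the method of Miettinen and Nurminen". None of these places names strata, weights or covariates. Protocol 10.8 does print a fixed-effect model with age strata under the heading on percentages, but that text concerns log-transformed titers and GMTs.

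**The concern.** Allocation is balanced on age by design, so an age effect on response adds almost nothing to the sampling error of a group difference. A crude two-sample interval takes its variance from the overall response rate, and that variance still includes the spread between the two strata. If adolescents and young adults respond at different rates, the interval is therefore wider than the design requires and covers more than the nominal 80%.

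What is at stake is some precision in the responder contrasts: same arm versus different arms, MenABCWY versus same arm, and the comparisons with the single-vaccine groups. No other planned analysis brings age into these endpoints, since Protocol 10.5.7 plans no subgroups. Any age imbalance left in PPS3 after exclusions would also go unadjusted, though the 50-per-stratum cap should keep it small.

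**Working it through.** **1. The plan's own figure.** No power or interval width is given for the percentages. The only stated calculation is for the pooled B-strain GMT: n = 100 per group, difference -0.130, SD 0.435 and a "significance level (alpha) of 10% using a 1-sided 2-sample equal-variance t-test". The noncentrality is 0.130 / (0.435 × √(2/100)) = 2.113 and the critical t on 198 df is 1.286, which gives power 0.796. This matches the 0.796 in Protocol Table 14. A one-sided 10% level corresponds to the 2-sided 80% interval used throughout.

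**2. Inputs for the percentages.** From the documents: 50 + 50 subjects per group and 2-sided 80% intervals. Assumed: the response rate in each age stratum, pA and pB, taken as equal in the two groups compared.

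**3. Large-sample arithmetic.** With equal strata and overall rate p = (pA + pB)/2, the crude per-subject variance is p(1 − p). The within-stratum variance is [pA(1 − pA) + pB(1 − pB)]/2. They differ by ((pA − pB)/2)². The width ratio r is the square root of within over crude, and the coverage of the crude interval is 2Φ(1.2816/r) − 1.

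| Stratum rates | Crude | Within | r | Coverage of crude 80% interval |
|---|---|---|---|---|
| 70/70% | 0.21 | 0.21 | 1.000 | 0.800 |
| 60/80% | 0.21 | 0.20 | 0.976 | 0.811 |
| 55/85% | 0.21 | 0.1875 | 0.945 | 0.825 |
| 50/90% | 0.21 | 0.17 | 0.900 | 0.846 |

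**4. Actual Miettinen-Nurminen widths.** These are score intervals with restricted maximum likelihood and the N/(N − 1) factor. The stratified version uses weights n1·n2/(n1 + n2). Widths are in percentage points at expected counts.

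| Stratum rates | Crude | Stratified | Ratio |
|---|---|---|---|
| 70/70% | 16.63 | 16.68 | 1.003 |
| 65/75% | 16.63 | 16.58 | 0.997 |
| 60/80% | 16.63 | 16.30 | 0.980 |
| 55/85% | 16.63 | 15.83 | 0.952 |
| 50/90% | 16.63 | 15.16 | 0.911 |
| 85/95% | 11.16 | 11.14 | 0.998 |
| 82/98% | 11.16 | 11.11 | 0.995 |

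The small loss at 70/70% comes from the finite-sample factor. It is 100/99 within a stratum against 200/199 overall, and √[(100/99)/(200/199)] = 1.0025.

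**5. Simulation, 2,000 trials per scenario.** The Monte Carlo standard error of coverage is about √(0.8 × 0.2/2000) = 0.009.

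| Stratum rates | Mean width ratio | Coverage, crude | Coverage, stratified |
|---|---|---|---|
| 70/70% | 1.000 | 0.81 | 0.81 |
| 65/75% | 0.995 | 0.81 | 0.81 |
| 60/80% | 0.978 | 0.83 | 0.82 |
| 50/90% | 0.910 | 0.84 | 0.79 |
| 85/95% | 0.996 | 0.81 | 0.80 |
| 80/98% | 0.989 | 0.81 | 0.79 |

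The crude interval does not undercover in any of these scenarios. At 60/80% most of its excess coverage is shared by the stratified interval, so only about 0.01 there comes from ignoring age. At 50/90% the contrast is clear.

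**The case against.** The strongest case against is that nothing is shown to be lost. The documents contain no response rate by age for any strain, group or visit. The gain is visible only with large age gaps at mid-range rates: even at 60/80% it is 16.63 − 16.30 = 0.33 of a percentage point. The crude interval is valid, Protocol 10.10 calls all analyses descriptive, and no margin or power is attached to the responder differences. All of this stands, and it sets the size of the point.

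Several stronger readings are tempting and not supported.

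- *The intervals are wider than they need be, as a fact.* This holds only if response differs by age.
- *The lymph-node conclusion is affected.* SAP 8.3.1 does label the same-arm versus different-arms difference a test for interference. However, the inferiority rule in SAP 8.1.1 and Protocol 10.8 uses the 80% interval of the GMT ratio, from models that already contain age stratum.
- *Stratifying would put the responder and GMT contrasts on one footing.* It would not. Center and baseline titer would remain in the GMT models only, and a dichotomised titer can disagree with a mean under any adjustment.
- *The plan rules out stratification.* It is silent. The unstratified reading is the natural one, because the method is named without strata or weights.

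The objection does not give a reason to leave the stratum out. Adding it costs at most about 0.3% of the width when age has no effect, and the trial already randomises by this factor.

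**Conclusion.** The point holds as a modest, conditional matter of precision. The design and the GMT/GMR models use age stratum; the responder differences, as written, do not. If response differs by age, the 80% intervals are valid but conservative.

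Under assumed rates that are equal in the two groups, with 50 + 50 subjects per group, a stratified interval is about 2% narrower at 60/80%, 5% at 55/85% and 9% at 50/90%. It is about 0.5% narrower or less for a 10-point gap and about 1% narrower or less near 90% response. With equal rates it is not narrower. Which of these applies, by strain and visit, cannot be settled from the documents.

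No validity problem follows, and no prespecified decision changes.

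**What to change.** In SAP 8.3.1, 8.3.2, 8.4.1 and 8.4.2, and in Protocol 10.8, state that the difference and its 2-sided 80% interval are computed by the Miettinen-Nurminen method stratified by age stratum, and name the weights. Keep the crude interval as supportive.

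Define the stratum as the one entered at randomisation. SAP 6.2 derives age from a birth date imputed as 30 June of the birth year. A 17-year-old with a birthday late in the year, vaccinated after 30 June of the year of turning 18, would be derived as 18 and could fall in the wrong stratum.

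Add a sentence saying that center, the minimisation factor, is left out of these intervals and why. The number and size of centers are not given, and small centers could make stratifying by center impractical.

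The cost is a sentence or two per section and a small programming change, with no new data. The choice should be fixed before results are seen, so that crude versus stratified is not decided afterwards.

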#### **8.3.2 Secondary Endpoint**

This endpoint will be summarized for PPS4.

The percentage of subjects with titers above the LLOQ as well as the associated 2-sided 80% Clopper-Pearson CIs [Clopper, 1934] will be computed by study group at AVISIT 2. Note that the MenACWY group is not included in the secondary analysis.

In addition, differences in percentages of subjects with titers above the LLOQ and 2-sided 80% CIs between selected study groups will be calculated using the method of Miettinen and Nurminen [Miettinen, 1985]. The following differences will be calculated:

- rMenBOMV+ACWY\_S versus rMenBOMV+ACWY\_D (test for immune interference, due to immunological stress to lymph node)
- MenABCWY versus rMenBOMV+ACWY\_S (test for other unknown immunological interference)
- rMenBOMV+ACWY\_S versus rMenBOMV
- rMenBOMV+ACWY\_D versus rMenBOMV
- MenABCWY versus rMenBOMV

No adjustments will be made for multiple comparisons.

## **8.4 Summary and Analysis of Percentage of Subjects With a 4-fold Increase in hSBA Titer**

### **8.4.1 Primary Endpoint**

This endpoint will be summarized for PPS3.

The analysis described in Section 8.3 will be repeated for subjects with a 4-fold increase in hSBA titer at AVISIT 4 since Baseline.

A 4-fold increase is defined as:

- a) for individuals whose pre-vaccination titers are < LOD, the post-vaccination titers must be  $\geq$ 4-fold the LOD or  $\geq$  the LLOQ, whichever is greater;
- b) for individuals whose pre-vaccination titers are  $\geq$  the LOD and < the LLOQ, the post-vaccination titers must be at least 4 times the LLOQ;
- c) for individuals whose pre-vaccination titers are  $\geq$  the LLOQ, the post-vaccination titers must be at least 4 times the pre-vaccination titer.

### **8.4.2 Secondary Endpoint**

This endpoint will be summarized for PPS4.

The analysis described in Section 8.3 will be repeated for subjects with a 4-fold increase in hSBA titer at AVISIT 2 since Baseline.

A 4-fold increase is defined as:

- a) for individuals whose pre-vaccination titers are < LOD, the post-vaccination titers must be  $\geq$ 4-fold the LOD or  $\geq$  the LLOQ, whichever is greater;
- b) for individuals whose pre-vaccination titers are  $\geq$  the LOD and < the LLOQ, the post-vaccination titers must be at least 4 times the LLOQ;
- c) for individuals whose pre-vaccination titers are  $\geq$  the LLOQ, the post-vaccination titers must be at least 4 times the pre-vaccination titer.

## 9 Safety Analysis

Adverse events summaries will be based on the Solicited Safety Set, the Unsolicited Safety Set and the Overall Safety Set as described below.

### 9.1 Adverse Events

Solicited AEs, unsolicited AEs, SAEs, medically attended AEs, AEs leading to withdrawal from treatment or from the study, and AEs of special interest (AESI) that occur post-vaccination will be summarized and also presented in listings. AEs occurring prior to a subject receiving any study vaccine will be listed only.

The definitions for SAEs and medically attended AEs and AESIs can be found in protocol sections 8.1.2 and 8.3.3.4 respectively. Further information about AESIs can be found in Section 9.1.3.

Incomplete onset dates and end dates for any AEs will be imputed to determine if the event occurred within the time period specified for AE summaries as described in sections 9.1.1, 9.1.2 and 9.1.3. Actual dates recorded will be presented in listings, imputed dates will not be presented. Incomplete dates will be imputed as follows:

Missing onset dates (where UK and UKN indicate unknown or missing day and month respectively):

- UK-MMM-YYYY: If the month and year are different from the month and year of the first dose of study vaccine, assume 01-MMM-YYYY. If the month and year are the same as the first dose of study vaccine month and year, and the end date (after any imputation) is on or after the first dose of study vaccine, then assume the date of the first dose of study vaccine. If the month and year are the same as the first dose of study vaccine month, and year and the end date (after any imputation) is prior to the first dose of study vaccine, then assume the end date for the onset date.
- DD-UKN-YYYY/UK-UKN-YYYY: If the year is before the year of first dose of study vaccine, assume DD-JAN-YYYY/01-JAN-YYYY of the collected year. If the year is after the first dose and the same as the second

dose, assume DD-JAN-YYYY/01-JAN-YYYY. If the year is the same as the first dose of study vaccine year, and the end date (after any imputation) is on or after the first dose of study vaccine, then assume the date of the first dose of study vaccine. If the year is the same as the first dose of study vaccine, and the end date (after any imputation) is prior to the first dose of study vaccine, then assume the end date for the onset date.

Missing end dates (where UK and UKN indicate unknown or missing day and month respectively):

- UK-MMM-YYYY: Assume the last day of the month.
- DD-UKN-YYYY: Assume DD-DEC-YYYY.
- UK-UKN-YYYY: Assume 31-DEC-YYYY.

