**Table 1 Visit Intervals**

Interval	Optimal length of interval	Allowed interval (Min – Max) 
Visit 1 (Day 1) → Safety call 1 (Day 15)	14 days	11 days – 17 days (Days 12 – 18)
Visit 1 (Day 1) → Visit 2 (Day 31)	30 days	23 days – 40 days (Days 24 – 41)
Visit 1 (Day 1) → Visit 3 (Day 61)	60 days	53 days – 70 days (Days 54 – 71)
Visit 3 (Day 61) → Safety call 2 (Day 75)	14 days	11 days – 17 days (Days 72 – 78)

Visit 3 (Day 61) → Visit 4 (Day 91)	30 days	23 days – 40 days (Days 84 – 101)
-------------------------------------	---------	-----------------------------------

Safety call time intervals will not be used for the assessment of protocol deviations. The Study Day ranges shown in the table are based on optimal intervals; the actual Study Day ranges for Safety Call 2 and Visit 4 will be based on when Visit 3 occurs.

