### Missing Data

For safety analyses, subjects who missed reporting symptoms (solicited or unsolicited) or concomitant medications will be analyzed to determine the missing mechanism. For the analysis of solicited symptoms, implausible measurements will not be replaced but they will be excluded from the analyses. Missing values will not be imputed for solicited/unsolicited AEs or concomitant medications.

In order to minimize the effect of missing data, the study period will be divided into time intervals for the safety analyses. For unsolicited AEs, the study period will be divided into the following intervals: all unsolicited AEs reported from day 1 to day 31 after vaccination (day of vaccination = day 1, Visit 1 and Visit 3 will be assessed separately and combined), medically attended AEs reported during the entire study period, AEs leading to premature withdrawal from the study during the entire study period, SAEs reported during the entire study period and AESI reported during the study period for the Unsolicited Safety Set.

Concomitant medications will be assessed for the entire study period for the Overall Safety Set.

Solicited AE data will be analyzed by the following intervals: 30 minutes post-vaccination on day of vaccination, 1 – 3 days post-vaccination (including the day of vaccination as day 1, excluding 30 minutes post-vaccination), 4 days – 7 days post-vaccination, and 1 day - 7 days (including the day of vaccination as day 1, excluding 30 minutes post-vaccination). Intervals will be assessed for Visit 1 and Visit 3, separately and combined, for the Solicited Safety Set. Solicited local AEs will be considered separately by vaccine for study groups where two vaccinations are administered at each visit, and also separately by location

A subject will be classified as having missing data within the specified intervals as described below:

- Solicited AEs
  - Temperature will be regarded as missing if “Temperature taken” = “No” at every time point within the interval (on Post-vaccination Body Temperature eCRF page).
  - Pain will be regarded as missing if no intensity values are recorded for Vaccine A and Vaccine B separately at every time point within the interval (on Vaccine A/Vaccine B Solicited Local Adverse Event eCRF pages). An intensity value of ‘None’ is a valid value and will not be considered a missing value.

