### **9.1.2 Unsolicited Adverse Events**

An unsolicited AE is an AE that was not solicited using a pDiary and that was spontaneously communicated by a subject/parent(s)/LAR(s) who has signed the informed consent or a solicited local or systemic that meets the criteria described in Section 9.1.1. Solicited AEs lasting more than 7 days after vaccination (including the day of vaccination) are also recorded as AEs.

The original verbatim terms used by investigators to identify AEs in the Adverse Events page of the eCRF will be mapped to preferred terms (PT) using MedDRA version 20.1 or higher. The AEs will then be grouped by MedDRA preferred terms according to system organ class (SOC).

Unsolicited AE summaries will be based on the Unsolicited Safety Set.

The following summaries will present the number and percentage of subjects reporting each AE and will be presented by SOC and PT for each study group, grouped by three time points: 30 days post-vaccination at any visit, 30 days post-vaccination at Visit 1 and 30 days post vaccination at Visit 3. Note that the MenACWY group will not be included in the 30 days post vaccination at Visit 3 summary):

- Any unsolicited AE
- Unsolicited AEs that are possibly or probably related to vaccine(s) - (Relationship to study treatment = Yes)
- Severity of unsolicited AE

Additional summaries will present the number and percentage of subjects reporting AEs in the following categories and will be presented by SOC and PT for each study group from Day1 through till end of study for the Overall Safety Set:

- AEs leading to withdrawal from the study
- AEs leading to withdrawal from the study vaccine
- AEs leading to a medically attended visit
- AEs leading to death
- SAEs
- SAEs that are possibly or probably related to vaccine(s)
- SAEs leading to death
- SAEs that are possibly or probably related to vaccines(s) and leading to death

Listings will be presented for Any AEs, AEs that are possibly or probably related to vaccine(s), AEs leading to withdrawal from the study, AEs leading to withdrawal from the study vaccine, AEs leading to medically attended visit, AEs leading to death, SAEs, SAEs that are possibly or probably related to vaccine(s), SAEs leading to death, SAEs that are possibly or probably related to vaccine(s)

and leading to death. AEs that were reported as occurring prior to a subject receiving any study vaccine will only be included on the Any AEs listing.

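### The partial-date rule for AE onset has no clause for dose 2, so unknown-day onsets in the month of dose 2 usually drop out of the Visit 3 table

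*SAP*

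**What the plan says.** SAP 9.1 gives the purpose of the rule: "Incomplete onset dates and end dates for any AEs will be imputed to determine if the event occurred within the time period specified". For an onset with month and year but no day (UK-MMM-YYYY) there are two cases.

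- **Month of dose 1.** The rule tests the end date, recorded or imputed. Where that date "is on or after the first dose of study vaccine, then assume the date of the first dose of study vaccine". An end date before dose 1 is itself used as the onset.
- **Any other month.** "If the month and year are different from the month and year of the first dose of study vaccine, assume 01-MMM-YYYY". Neither the date of dose 2 nor the end date is checked.

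Dose 2 is mentioned in the onset rules only where the month is also unknown, and only by year.

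SAP 9.1.2 tabulates all unsolicited AEs, related unsolicited AEs and severity for three periods: "30 days post-vaccination at any visit, 30 days post-vaccination at Visit 1 and 30 days post vaccination at Visit 3". SAP 4.3 (Missing Data) defines the interval as "all unsolicited AEs reported from day 1 to day 31 after vaccination", with the vaccination day as day 1. SAP 9.1.2 also has a table of non-serious events within 30 days after any visit. SAP Table 1 puts Visit 3 60 days after Visit 1, with 53 to 70 days allowed.

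**The concern.** The rule exists to put events in the right window. It does so around dose 1 and fails around dose 2. An event dated only to the month of dose 2 is moved to the 1st, usually before dose 2 and more than 30 days after dose 1, even when its recorded end date is after dose 2. Neither document has a later step that moves it back.

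At stake is the count of unsolicited AEs, related AEs and severity after the second dose in the four two-dose groups, one of which receives the investigational vaccine. The single-dose MenACWY group has no dose 2 and cannot lose events this way.

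**Working it through.** The documents give no figure for this point, so there is none to reproduce. The rule was applied literally to calendar dates.

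**Inputs.** Dose interval of 53 to 70 days, optimum 60 (SAP Table 1). Window of 0 to 30 days after each dose (SAP 3.2.2 and 4.3). Imputation rule from SAP 9.1. Assumption: every dose-1 date in 2018 to 2021, equally weighted, used only to cover the month lengths.

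**Step 1: which branch applies.** Dose 2 is at least 53 days after dose 1 and no month exceeds 31 days, so dose 2 never falls in the month of dose 1. The 01-MMM branch always applies to the month of dose 2.

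**Step 2: example.** Dose 1 on 16 July, dose 2 on 14 September, onset recorded as UK-SEP. The imputed onset is 1 September, study day 48, which is 13 days before dose 2. It is outside Day 1 to 31 and outside the dose-2 window.

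**Step 3: unknown-day onset in the month of dose 2.** Share of dose-date combinations by where the imputed date lands:

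| Interval | Neither window | Visit 1 window | Visit 3 window |
|---|---|---|---|
| 53 days | 72.3% | 24.4% | 3.3% |
| 60 days | 94.8% | 1.9% | 3.3% |
| 70 days | 96.7% | 0% | 3.3% |
| 53 to 70 days | 90.9% | 5.8% | 3.3% |

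The 3.3% is dose 2 given on the 1st. The Visit 1 entries arise when dose 2 falls late in the month: from the 24th at 53 days, only on the 31st at 60 days. With a 0 to 29 day window the pooled figure for neither is 92.3%; with weekday dosing only it is 91.0%.

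**Step 4: all unknown-day onsets truly in the Visit 3 window.** Assume uniform onset over the 31 window days. Then 50.7% of those days lie in the month of dose 2. The rest lie in the following month, whose 1st is always inside the window, so they are kept. Weighted by possible onset days, 6.36% of the dose-2-month days belong to subjects dosed on the 1st and are also kept.

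Share lost from the Visit 3 table = 0.507 × (1 − 0.0636) = 0.475.

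If onsets cluster just after dose 2 the share is higher. In the limit of onset on the vaccination day it is 1 − 0.033 = 96.7%.

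**Step 5: any-visit table.** Apply the rule to every onset day from dose 1 to 30 days after dose 2, with uniform onset, unknown day and end date on or after dose 1. At 60 days there are 91 possible days, of which 31 + 31 = 62 (68.1%) are truly in a window. The rule wrongly removes 16.2% of all days from the Visit 3 window. It wrongly adds 16.2% to the Visit 1 window, because onsets between the windows in the month after dose 1 are also pulled back to the 1st. The imputed any-visit share is 68.1%, equal to the true share. Over 53 to 70 days both are 67.0%.

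**The case against.** The case for leaving the rule alone has five parts.

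- **The 91% is conditional.** A reader might infer that nine in ten post-dose-2 events with an unknown day are lost. The figure applies only to unknown-day onsets in the month of dose 2. Across the whole Visit 3 window the loss is about 47% under uniform onset. Also, about 48% of the days in the month of dose 2 precede dose 2, and keeping those events out of the Visit 3 window is correct. This stands.
- **Direction.** A reader might infer that the rule lowers AE counts throughout. Step 5 does not support that for the any-visit table: losses and gains cancel under uniform onset. A net loss there requires clustering of onsets after doses. The under-count in the Visit 3 table remains either way.
- **Unknown month.** A reader might extend the criticism to the branch beginning "If the year is the same as the first dose of study vaccine year" and say that it credits every event in that year to dose 1. It has an end-date condition, and events ending before dose 1 take their end date. A post-dose-2 event moved to the dose-1 date also stays in the any-visit table. A year-only onset is improbable in a 91-day study with contacts on Days 15, 31, 61, 75 and 91. This part is not pursued.
- **Reach.** SAEs, deaths, withdrawals and medically attended AEs are summarized to the end of study and AESIs to Day 91. Solicited AEs come from a daily diary. Listings keep every AE with its recorded date. All four two-dose groups share the rule, so it does not by itself tilt comparisons among them.
- **Frequency.** Safety Call 2, 11 to 17 days after dose 2, collects unsolicited AEs, so unknown days should be uncommon.

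The last two limit the consequence. They do not make the rule correct for dose 2.

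**Conclusion.** The rule is wrong as written, and the severity is minor. SAP 9.1 has no dose-2 counterpart to its dose-1 clause, so it under-counts post-dose-2 unsolicited AEs in the Visit 3 tables of the four two-dose groups. An unknown-day onset in the month of dose 2 lands in neither window for about 91% of dose-date combinations (72% to 97% by interval), and about 47% of unknown-day onsets truly in the Visit 3 window leave that table.

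The first figure assumes dose-1 dates spread evenly over the calendar and equal weight for each allowed interval. The second also assumes uniform onset within the window. The effect on actual counts cannot be computed, because the documents do not say how many onset dates will be partial. No net bias in the any-visit table is shown unless onsets cluster after vaccination.

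**What to change.** Add one clause to the UK-MMM-YYYY onset rule in SAP 9.1: *where the month and year of the partial onset match those of the second dose, and the end date (after any imputation) is on or after the second dose or the event is ongoing, set the onset to the date of the second dose; otherwise use 01-MMM-YYYY.*

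Every unknown-day onset truly in the Visit 3 window then stays there, and the loss falls from about 47% to zero. The cost is one sentence and a few lines of code.

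The downside is that events that began earlier in that month and lasted to dose 2 will be counted after dose 2. This is the same conservative choice the SAP already makes for dose 1. The any-visit table also loses its offset. At a 60-day interval with uniform onset, restoring the lost 16.2% raises the imputed share of unknown-day onsets to at least 68.1% + 16.2% = 84.3%, against a true 68.1%. That is an over-count in the cautious direction and is confined to partial dates.

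No change to the unknown-month rule is proposed. Reporting the number of imputed onset dates by group and visit would show whether any of this matters.
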